### 7.5 Emergency Unblinding

Emergency unblinding will be overseen by the authority of the TMG. In the event that emergency unblinding is required the linked dataset will be accessed by an independent administrator from the PROTECT study team (outside of the VitaMIND study team) using the participant identifier via the administration portal on the PROTECT site to reveal treatment allocation of the individual participant. Access permissions for the administration portal will be restricted to the VitaMIND trial coordinator and supporting administrator in the PROTECT team (who will act as the independent administrator in the event of unblinding). Access to the portal does not automatically provide access to personal details, as this is password-protected in a separate database. Passwords will be held by the Trial Coordinator, under the supervision of the Chief Investigator, and will only be approved for use where required for safety and unblinding procedures.

### 7.6 Baseline data

Participant data will be pulled from the PROTECT main dataset to populate the baseline data point. This will include:

- Age
- Gender
- Education level
- 
- Use of brain training games prior to randomisation (not an eligibility or randomisation factor – for use in analysis only)
- Lifestyle factors as captured by the PROTECT lifestyle questionnaire (not an eligibility or randomisation factor – for use in analysis only)

Cognitive Assessment data and all other trial-specific measures will be collected within the trial areas as part of the scheduled assessment at baseline.

### 7.7 Trial assessments

Assessments will be conducted at baseline, 26, 52, and 104 weeks. Participants will receive weekly automated emails notifying them that assessments are available to complete until they are completed or no longer available. The assessments will become available for completion two weeks before the assessment point and remain open for completion during the week of the assessment point and a further five weeks, making them available for eight weeks in total. Missing data or late data will be accounted for within the analysis plan.

Assessments will follow the set online assessment protocol described below.

1. scale Trail-making B (primary outcome measure)
2. PROTECT Cognitive Tests: Switching Stroop Test, Baddeley Grammatical Reasoning , Self-ordered Search, Digit Span, and Paired Associate Learning Tasks (secondary outcome measures)
3. Instrumental Activities of Daily Living
4. EQ5D measure of health and wellbeing
5. Mild Behaviour Impairment Scale

An anonymous survey will be completed at the end of the study to provide a process measure and to capture participant experience.

## 7.8 Withdrawal criteria

### Withdrawal by participant

Participants are free to withdraw from the trial at any point without giving a reason. This can be achieved by selecting the withdrawal option on the study website or by contacting the study team by email or telephone.

### Withdrawal due to non-compliance

Any participant not fulfilling criteria for compliance after one week will be withdrawn from the trial. Compliance will be established by a telephone call at the one-week time point in which participants will be asked to confirm they are taking their Vitamin D study tablets. This will be recorded in REDCap Cloud by the study administrator.

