### Withdrawal due to loss of capacity

Cognitive status would usually be monitored by a medical practitioner at a clinical visit using a clinical assessment tool such as the Mini-Mental State Examination (MMSE) or similar. Since this study is conducted remotely, cognitive ability of participants will be monitored through an existing algorithm which is built into the PROTECT system. It is based on completion of the cognitive tests described above which are considerably more sensitive to change than the MMSE. Any participant flagging as performed more than one standard deviation below age-matched norms on two cognitive tests in two consecutive assessments will be reviewed by one of two named study doctors ([name] / [name]). If concerns are considered to be valid the participant and their GP will be contacted by the study doctors to recommend further assessment, and the participant will be withdrawn from the trial.

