### Withdrawal procedure

At the point of withdrawal participants will receive notification by email. Anonymised data will be retained. Participants will have the option to remove all personal data with the exception of the minimum required for record of consent. Participants will be sent a pre-paid envelope to return any unused tablets for disposal.

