### 8.5 Preparation and labelling of Supplement

Blister packs of study supplements will be labelled with the participant ID and batch number. The Clinical Trials Unit at the University of Exeter will provide recording and mail-out services. The CTU is fully registered and qualified as a research facility and is fully compliant in participant confidentiality procedures. Postage will comply with regulations pertaining to mailing of research/hazardous materials, using pre-labelled envelopes, sealed boxes and tracked delivery. The randomisation schedule will be directly accessed through REDCap Cloud by the Clinical Trials Unit staff member who will be unblinded to treatment allocation. This staff member will be responsible for labelling and sending out trial tablets, recording dispensing and reporting back to the VitaMIND team to ensure dispensing activity is recorded in the study database.

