#### Absent participant follow-up

In the event that a participant who has entered the intention-to-treat cohort fails to complete any online activity on two consecutive timepoints they will be contacted by telephone by a study administrator. The purpose of the call will be to verify the health and wellbeing of the participant. If any suspected AE is detected this will prompt an AE report.

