## 10.3 Statistical analysis plan

All statistical analyses will be undertaken according to a predefined detailed statistical analysis plan (SAP) agreed in advance with the trial management group, trial steering committee.

Baseline sociodemographic and outcome variables will be reported and compared descriptively by treatment arm.

The primary analysis will be conducted on an intention-to-treat basis comparing both primary and secondary outcomes between treatment and control groups in those with complete data at week 104 follow up. Linear regression models will adjust for baseline score and stratification variables.

Secondary analyses will include: between group comparisons at all follow up time points using mixed model repeated measures approach; between group comparison of primary and secondary outcomes at primary outcome time point based on imputed outcome data (using multiple imputation models based on an assumption that data is missing at random); per-protocol analysis using an estimated complier average causal effects analysis (CACE) of the primary outcome at the primary outcome follow-up data; and an exploratory assessment of subgroup effects using interaction terms based on subgroup effects. Prior to analysis and to be defined in the SAP, the trial management group will pre specify the per-protocol definition and subgroup.

All analyses will be undertaken by a statistician blinded to group allocation. Results will be reported means and 95% CIs.

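### Randomised participants who fail a one-week compliance call are withdrawn from the trial itself, so the week-104 comparison called intention-to-treat leaves them out

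*Protocol*

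**What the plan says.** Randomisation takes place after consent (Protocol 7.3). Tablets are then labelled and posted according to allocation: "The randomisation schedule will be directly accessed through REDCap Cloud by the Clinical Trials Unit staff member who will be unblinded to treatment allocation" (8.5). One week later participants are telephoned and asked whether they are taking the tablets. The consequence of failing is stated in 7.8: "Any participant not fulfilling criteria for compliance after one week will be withdrawn from the trial".

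The withdrawal procedure in 7.8 consists of an email notice, a statement that "Anonymised data will be retained", an option to have personal data removed, and the return of unused tablets. It does not separate stopping tablets from leaving follow-up, and it schedules no further assessments.

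Section 10.3 says "The primary analysis will be conducted on an intention-to-treat basis". The same sentence then restricts who is analysed, since the work consists of "comparing both primary and secondary outcomes between treatment and control groups in those with complete data at week 104 follow up". Multiple imputation is a secondary analysis, "using multiple imputation models based on an assumption that data is missing at random". A complier average causal effect (CACE) analysis is also secondary. Section 9.3 refers to the case where "a participant who has entered the intention-to-treat cohort fails to complete any online activity on two consecutive timepoints", but does not say when a participant enters that cohort.

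**The concern.** An intention-to-treat comparison takes everyone as randomised, whatever they do with their tablets. Here a post-randomisation behaviour, not confirming tablet-taking at one week, leads by rule to removal from the trial. Ordinary dropout happens despite the plan. This loss is written into it, and no statistical analysis plan can recover outcomes that the protocol stops collecting.

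What is at stake is the question being answered. A reader of the report would take the result as the effect of offering vitamin D to all who were randomised. It would be the effect in a group selected in part for having started tablets, which is somewhat larger if the supplement works.

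**Working it through.** **Does the call follow randomisation?** Consent, then randomisation (7.3), then posting by allocation (8.5), then the call about those tablets (7.8). Yes.

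**Can someone who fails the call enter the primary analysis?** That analysis needs week-104 data (10.3). Section 7.8 withdraws the person from the trial, and its procedure provides no assessment afterwards. On the plain reading, no. The protocol does not say in so many words that assessments stop.

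**The plan's own figure.** Inputs from 10.1: effect 0.3 SD, two-sided 0.05, 90% power, 20% drop-out. The two-sample calculation gives 234 per group, as stated. 234 / 0.8 = 292.5, so 293 per group; 468 / 0.8 = 585 in total, against the stated 584. The sample size reproduces and is not in dispute.

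**Effect in all randomised.** The failure rate r is not in the protocol; 2-10% is an assumption. Take 584 / 2 = 292 per arm and 0.30 SD in those kept.

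- If those who fail never take tablets, the effect in all randomised is 0.30 × (1 − r).
- If they would later get half the benefit, it is 0.30 × (1 − r/2).

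| r | failing per arm (292r) | failing in total (584r) | never take tablets | half benefit |
|---|---|---|---|---|
| 2% | 5.8 | 11.7 | 0.294 | 0.297 |
| 5% | 14.6 | 29.2 | 0.285 | 0.2925 |
| 10% | 29.2 | 58.4 | 0.270 | 0.285 |

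**Does missing-at-random imputation repair this?** One-week failures have only baseline data. If the model uses arm and baseline alone, their outcomes are borrowed from people in the same arm who passed the call. A simulation with 1 million per arm, an assumed baseline correlation of 0.6 and failures who never take tablets gave:

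| r | all randomised | kept | after imputation |
|---|---|---|---|
| 2% | 0.293 | 0.299 | 0.299 |
| 5% | 0.286 | 0.301 | 0.301 |
| 10% | 0.272 | 0.303 | 0.302 |

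Imputation returns the effect in those kept.

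**Power if they are retained.** Suppose the failures fall within the planned 20% loss and, once retained, complete week 104. They then add to the 234 per group. Power is approximately Φ(d × √(n/2) − 1.96).

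- r = 5%: n = 234 + 14.6 ≈ 249, d = 0.285, power about 89%.
- r = 10%: n = 234 + 29.2 ≈ 263, d = 0.270, power about 87%.

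If retention added no analysed participants (n = 234), the figures would be 86.9% and 83.2%.

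**The case against.** **The size is small and every rate is assumed.** Participants had just completed a deliberate multi-step consent (7.2) and the test is self-report, so few may fail. With 234 per group the unadjusted standard error is √(2/234) = 0.092 SD, so a gap of 0.006-0.030 SD is 0.07-0.32 standard errors. This stands, and it limits the point to a modest one.

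**Most of the gap between label and analysed set comes from 10.3 itself,** which openly restricts the comparison to those with week-104 data, with 20% loss planned. This also stands. It would be wrong to say that the comparison simply covers everyone who passed the call; the analysed group is narrower.

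**Missing data belong to the analysis plan.** Section 7.7 defers them, and 10.3 names no imputation variables. The criticism of imputation is therefore conditional on a model with arm and baseline only. A different imputation could approximate the all-randomised effect, but by assumption and not from observed outcomes. The analysis-set definition may also sit in the SAP, but whether outcomes are collected is a protocol matter.

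**Outcomes might be recovered from the PROTECT cohort,** whose members complete annual cognitive assessments. This is a possible route, but the protocol does not commit to it, and 7.6 says that cognitive and trial-specific measures are collected within the trial areas.

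**Stronger readings a reader might infer.** One is that the rule biases the arms against each other or inflates false positives. The call applies alike to both blinded arms at one week, so failure should be roughly balanced; nothing in the protocol points to differential failure. Balanced exclusion would not bias the CACE estimate either. Another is that the capacity rule in 7.8, under which doctors contact the participant and GP "to recommend further assessment, and the participant will be withdrawn from the trial", compounds the problem. That is a doctor-reviewed safeguard, not a compliance rule. The protocol gives no rates from which to size it, and under assumed rates its effect is towards a smaller estimate, so it does not support this point.

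**Conclusion.** The point holds, at modest size. The protocol removes randomised participants from the trial for a post-randomisation behaviour and then calls the week-104 comparison intention-to-treat. That comparison estimates the effect in participants who passed the call, were not otherwise withdrawn and completed week 104.

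The consequence is a mislabelled estimand and an overstatement of the all-randomised effect by 0.006-0.030 SD. This range assumes 2-10% failure, no tablets ever taken by those who fail, and 0.30 SD in those kept; half benefit would halve it. The conclusion also rests on reading withdrawal from the trial as the end of assessments, which is the plain meaning but is not spelled out. It should be fixed because the remedy is cheap and the label would otherwise mislead. It does not threaten the validity of the comparison between arms.

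**What to change.** Amend the non-compliance paragraph of 7.8 along these lines: a participant who does not confirm tablet-taking at the one-week call is recorded as non-compliant and may stop tablets, but remains in the trial and is offered the 26-, 52- and 104-week online assessments unless they decline. Analyse these participants in their allocated arm and count them as non-compliers in the CACE analysis.

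The cost is an ethics amendment, some extra reminder emails through the automated system already described in 7.7, and a slightly diluted effect, with power of about 87-89% at 5-10% failure if those retained complete week 104.

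Version 8.0 dates from May 2023, and Appendix A says that power for the two-year outcome had already been reached, so most one-week calls are probably past. At minimum:

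- report one-week withdrawals by arm;
- with ethics approval, offer the week-104 assessment to those already withdrawn whose window is still open;
- where outcomes cannot be recovered, describe the 10.3 result as the effect in participants who passed the one-week call and completed week 104, not as intention-to-treat in all randomised.

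The reporting and wording steps cost almost nothing. Recontact carries some burden, since these people have been told that they were withdrawn and some may have had personal data removed.

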## 9.3 Recording and reporting of AEs and SAEs

All AEs and SAEs occurring from the time of **start of trial treatment** until the end of the trial will be reported by participants using an online form. Participants will be prompted to enter any details of events at each login event (quarterly) and encouraged to report any event proactively using the online form or by contacting the study team by telephone and email. All AEs will be logged in REDCap Cloud.

Receipt of an AE or SAE on the system will prompt review by the study team. AEs will be reviewed by at least two members of the TMG. SAEs will be reviewed by a study clinician within

24 hours. The participant, and their GP where appropriate, will be contacted for follow-up and recommended action. The Sponsor will also be informed.

AE and SAE actions and monitoring will be recorded electronically, including the following information

- full details in medical terms and case description
- event duration (start and end dates, if applicable)
- action taken
- outcome
- seriousness criteria
- causality (i.e. relatedness to trial drug / investigation), in the opinion of the investigator
- whether the event would be considered anticipated.

Any change of condition or other follow-up information will be faxed to the Sponsor as soon as it is available or at least within 24 hours of the information becoming available. Events will be followed up until the event has resolved or a final outcome has been reached.

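### Neither the one-week compliance call nor any withdrawal route asks about adverse events or the reason for stopping, so events behind early or between-prompt withdrawal are recorded only if volunteered

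*Protocol*

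**What the plan says.** Four parts of the protocol bear on this.

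- **One-week call (7.8, Withdrawal due to non-compliance).** The rule is "Any participant not fulfilling criteria for compliance after one week will be withdrawn from the trial". Compliance is established by telephone, and the only stated content of the call is that "participants will be asked to confirm they are taking their Vitamin D study tablets".
- **Self-withdrawal (7.8, Withdrawal by participant).** "Participants are free to withdraw from the trial at any point without giving a reason". The routes are a website option, email or telephone. No question accompanies any of them.
- **Withdrawal procedure (7.8).** "At the point of withdrawal participants will receive notification by email. Anonymised data will be retained". The rest of the procedure covers optional removal of personal data and return of unused capsules. No adverse-event enquiry is listed.
- **Adverse-event capture (9.3, and the table in 3.7).** The window runs from the start of treatment: events "until the end of the trial will be reported by participants using an online form". Solicitation is periodic: "Participants will be prompted to enter any details of events at each login event (quarterly". Between prompts, participants are "encouraged to report any event proactively using the online form or by contacting the study team by telephone and email".

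The table in 3.7 lists monitoring of safety and compliance as a tertiary objective. Section 9.4 asks the Trial Management Group to look for patterns in the accumulated safety data.

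**The concern.** Withdrawal is the moment at which an adverse event is most likely to explain what the participant is doing, and it may be the last contact. The participant may also have personal data removed at that point, after which re-contact may be impossible. As written, the protocol speaks to the participant at week 1, or receives a withdrawal message, and closes the record without asking whether anything happened.

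At stake is the completeness of the safety data that the Trial Management Group reviews. Events that lead people to stop are central to tolerability. A later analysis cannot recover events that nobody asked about, so this has to be settled in data collection and not in the statistical analysis plan. If the supplement did cause such events, the missing reports would fall more heavily in the active arm, and any tabulation by arm would lean towards no harm. That last step is conditional; nothing in the protocol shows that it occurs.

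**Working it through.** The protocol gives no figure on this point to reproduce, so the check consists of setting the sections side by side and doing simple timing arithmetic.

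**Step 1: timing of a compliance withdrawal.** The call is at week 1 (7.8). Prompts are quarterly (9.3), so the first falls at about 52/4 = week 13. The gap is 13 − 1 = 12 weeks. A participant withdrawn at the call has had no solicited adverse-event enquiry.

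**Step 2: timing of a self-withdrawal.** A participant who leaves between prompts is not asked about the time since the last one. If withdrawal falls at random within a quarter (an assumption), the unprompted time averages 13/2 = 6.5 weeks.

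**Step 3: who is and is not affected.**

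| Situation | Withdrawn by rule? | Solicited adverse-event question about the period of stopping? |
|---|---|---|
| Not taking capsules at the one-week call | Yes (7.8) | None stated |
| Withdraws personally, between prompts | Own choice (7.8) | None stated |
| Stops capsules after week 1, stays in the trial | No; quarterly tablet count only (8.11) | Yes, at the next quarterly prompt (9.3) |

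The gap is in the first two rows only.

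**Step 4: does the telephone safety net close it?** Section 9.3 (Absent participant follow-up) has an administrator ring a participant in the intention-to-treat cohort who shows no online activity at two consecutive timepoints. It does not say whether withdrawn participants are included. Even if they are, the earliest call would come at about 2 × 13 = week 26 if a timepoint is a quarterly login, or at week 52 if it is an assessment (7.7 sets these at weeks 26, 52 and 104).

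**Step 5: how many participants?** The protocol states no week-1 stopping rate. Taking 1% to 5% as an assumed range for those failing the call, 0.01 × 584 = 5.8 and 0.05 × 584 = 29.2, so about 6 to 29 participants would leave before any prompt. The share who stopped because of a health event is unknown.

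**Step 6: can an effect on a comparison by arm be quantified?** Only by inventing rates. With 584/2 = 292 per arm, an assumed 6% versus 2% stopping because of an event is about 18 versus 6, Fisher p = 0.020. Halving both rates gives about 9 versus 3, p = 0.14. The same ratio falls on either side of 0.05 depending on a rate that the protocol does not supply, so neither figure measures the loss.

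**The case against.** The strongest case on the other side has five parts.

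- **Proactive reporting is open throughout.** Section 9.3 invites reports by form, telephone or email at any time, and the one-week call is itself a contact with the study team. This stands: loss is a risk and not a certainty. It does not close the gap, because a volunteered report is not a solicited one.
- **The operational definition is narrow.** Section 9.2 counts only events needing medical intervention. A milder side effect that makes someone stop would not be an adverse event even if asked about. This stands, and it means that some of the missing information comes from the definition and not from the call. It is why answers below the definition should be kept as the reason for withdrawal.
- **Reported events are already followed to resolution** (9.3), with no exception for withdrawal. This stands, and nothing further is needed there.
- **Call scripts and web forms often sit in working documents.** True, and the protocol does not forbid other questions. But section 7.8 does set out the content of the call and the steps at withdrawal, and a team following it as written would not ask.
- **It may be late.** The amendment history for version 8.0 (May 2023) says that power for the two-year outcome had already been reached, which suggests that most one-week calls were over. This limits the benefit, chiefly to later withdrawals.

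A reader might infer that everyone who stops capsules because of a side effect is withdrawn unasked. The documents do not support that: compulsory withdrawal for non-compliance applies only at the one-week call, and later stoppers who remain in the trial still receive prompts. A reader might also infer that a planned safety comparison is biased. The protocol sets a monitoring objective and defines no between-arm safety test.

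**Conclusion.** The point holds in a limited form. For participants withdrawn at the one-week call, and for those who withdraw themselves between prompts, the protocol states no adverse-event or reason-for-stopping question, so an event behind the withdrawal enters the record only if it is volunteered. This weakens the tertiary safety-monitoring objective. It does not touch the primary outcome.

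The size cannot be given. What the text supports is a 12-week interval between the compliance withdrawal and the first prompt. The head count in step 5 and the average interval in step 2 rest on stated assumptions. A claim that a harm signal would be missed goes beyond the documents. The conclusion assumes that the call and the withdrawal forms are run as section 7.8 describes them, with no further questions in an undisclosed script. It is a cheap improvement worth making, not a fatal defect.

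**What to change.** Ask the standard adverse-event question at the one-week call and at every withdrawal route (website option, email, telephone) before the record is closed. Add an optional item on whether stopping was health-related. Log answers that meet the section 9.2 definitions as adverse or serious adverse events, and record the others as the reason for withdrawal. State in section 9.3 whether the absent-participant call covers withdrawn participants.

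The cost is one extra question on an existing call and on each withdrawal route, plus a minor amendment. It helps only calls and withdrawals still to come. The right to leave without giving a reason is kept because the item on stopping is optional, and no clinical rule changes.
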